5.3 Concomitant Medications/Treatments

Medications or vaccinations specifically prohibited in the exclusion criteria are not allowed during the ongoing trial. If there is a clinical indication for any medication or vaccination specifically prohibited during the trial, discontinuation from trial therapy or vaccination may be required. The investigator should discuss any questions regarding this with the Study PI. The final decision on any supportive therapy or vaccination rests with the investigator and/or the subject's primary physician. However, the decision to continue the subject on trial therapy or vaccination schedule requires the mutual agreement of the investigator, the Sponsor-Investigator and the subject.

Use of bisphosphonates/RANKL inhibitors are standard in CRPC and are allowed on the study. Starting bisphosphonates if indicated is allowed while on study.

Subjects are prohibited from receiving the following therapies during the Screening and Treatment Phase of this trial:

- Antineoplastic systemic chemotherapy or biological therapy except for ongoing androgen deprivation therapy (e.g. with LHRH agonist/antagonist)
- Immunotherapy not specified in this protocol
- Chemotherapy not specified in this protocol
- Investigational agents other than checkpoint inhibitor immunotherapy
- 5 α-reductase inhibitors (e.g., finasteride, dutasteride)
- Any herbal product known to decrease PSA levels (e.g. Saw Palmetto and PC-SPES)
- Neulasta®
- Radiation therapy
- Local intervention is discouraged unless medically unavoidable. Radiation therapy to a symptomatic solitary lesion/area may be considered on a case-by-case basis after consultation with the Principal Investigator (except during screening). Subjects receiving local intervention (e.g., palliative radiation) are allowed to continue to receive study treatment at the investigator's discretion. Subjects who receive local intervention may be considered not evaluable (and may be assigned a conservative censoring or progression date).
- Live vaccines within 30 days prior registration and while participating the trial. Examples of live vaccines include, but are not limited to, the following: measles, mumps, rubella, varicella/zoster, yellow fever, intranasal influenza, rabies, BCG (tuberculosis vaccine), and typhoid vaccine. If precluded by local regulations, live vaccines should not be given for 120 days after the last dose of checkpoint inhibitor immunotherapy is administered.
- Systemic glucocorticoids or other immunosuppressive drugs for any purpose other than to modulate symptoms from a drug-related AE of immunologic etiology (refer to Section 5.2 –

Dose Modification). The use of physiologic doses of corticosteroids may be approved after consultation with the Study PI.

- Use of prophylactic corticosteroids to avoid allergic and other adverse reactions (e.g., to IV contrast dye or transfusions) is permitted.
- Use of intermittent inhaled steroids or local injection of corticosteroids into joints is permitted upon consultation with the Study PI.
- Physiologic doses of prednisone ≤10 mg (or equivalent) per day.

5.4 Duration of Therapy

In the absence of treatment delays due to adverse events, treatment may continue for a total of 104 weeks in all from the start of study therapy or until one of the following criteria apply:

- Disease progression as defined in Section 7.0
- Inter-current illness that prevents further administration of treatment
- Unacceptable adverse event(s)
- Patient voluntarily withdraws from treatment
- General or specific changes in the patient's condition render the patient unacceptable for further treatment in the judgment of the investigator

Do not hold scans, continue scan schedule every 12 weeks from cycle 5 day 1 regardless of treatment delays thereafter.

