5.0 TREATMENT PLAN

5.1 Treatment Dosage and Administration

Protocol treatment must start within 14 business days of enrollment to the study.

- 5.1.1 In this study, Cohort A and Cohort B patients will start treatment with nivolumab dosed at 3 mg/kg IV and ipilimumab 1 mg/kg every 3 weeks for up to 4 doses. Cohort C patients will receive immunotherapy with nivolumab dosed at a flat dose of 480 mg IV every 4 weeks for up to 26 doses or 104 weeks.
- 5.1.2. Cohorts A and B maintenance immunotherapy with nivolumab dosed at a flat dose of 480 mg IV every 4 weeks will be continued for up to 23 doses or 92 weeks. Missed doses of 480 mg Nivolumab due to toxicity or general health condition will be skipped.

5.1.3 Total protocol therapy for all Cohorts will be up to 104 weeks during treatment. If disease progression or recurrence occurs during the follow-up phase, then per treating physician discretion, the patient may resume nivolumab 480 mg IV every 4 weeks until progression if tolerated with axial imaging as per protocol every, 12 weeks.

5.1.4 All study therapy will be administered on an outpatient basis.

Agent	Precautions	Dose	Route	Schedule	Cycle Length
Nivolumab (solution for injection) induction Cohort A and B only	Administer before other immunotherapy agents	3 mg/kg up to 4 doses	IV infusion over 30 minutes, +/- 10 minutes, with a sterile, nonpyrogenic, low protein binding 0.2 to 1.2 micrometer in-line filter. Follow with saline flush.	Day 1	3 weeks
Ipilimumab (solution for injection) induction Cohort A and B only	Administer 30 minutes after nivolumab.	1 mg/kg up to 4 doses	IV infusion over 90 minutes, +/- 10 minutes, through a non-pyrogenic, low protein-binding in-line filter. Separate IV line required.	Day 1	3 weeks
Nivolumab (solution for injection) maintenance After induction in Cohorts A and B; and throughout in Cohort C	Administer before other immunotherapy agents	480 mg up to 23 doses (92 weeks in Cohort A and B, and 104 weeks in Cohort C)	IV infusion over 30 minutes, +/- 10 minutes, with a sterile, nonpyrogenic, low protein binding 0.2 to 1.2 micrometer in-line filter. Follow with saline flush.	Day 1	4 weeks

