5.2 Toxities and Dosing Delays/Dose Modifications

Any patient who receives treatment on this protocol will be evaluable for toxicity. Each patient will be assessed for the development of toxicity according to the Time and Events Table (Section 6.1). Toxicity will be assessed according to the NCI Common Terminology Criteria for Adverse Events (CTCAE), version 4.03. Dose changes of either study drug is NOT permitted. Doses can be held however as necessary. Dosing holds should be made according to the system showing the greatest degree of toxicity.

Adverse Event Related vs Unrelated Dose Delays: If dose delay is due to an unrelated Adverse Event then reason for hold must be documented. Any patient on this protocol will be allowed to continue to receive study treatment at the investigator's discretion, regardless of AE relatedness. Do not have to delay dose for unrelated Adverse Event.

5.2.1 Treatment delay for toxicity of more than 84 days from last intended therapy will result in treatment discontinuation for the specific drug(s) responsible for the toxicity. If ipilimumab is permanently discontinued, then discontinue Nivolumab 3mg/kg. Nivolumab 480 mg can be continued.

5.2.2 Investigators should consider dose re-calculation of ipilimumab with change in weight as per standard of care/institutional guidelines. However, a change in weight by 10% or more should lead to a dose re-calculation.

5.2.3 Nivolumab and/or ipilimumab cannot be dose reduced in response to toxicity, and can only be held or discontinued as per detailed algorithms for immune-therapy toxicity management below.

NCI CTCAE v 4 Grade	Nivolumab	Ipilimumab
0-1	No change from original starting dose	No change from original starting dose
2	Withhold drug, resume treatment when adverse reaction improves to grade 0 or 1	Withhold drug, resume treatment when adverse reaction improves to grade 0 or 1
3	Withhold drug, resume treatment when adverse reaction improves to grade 0 or 1 when given as a single agent	Withhold drug, resume treatment when adverse reaction improves to grade 0 or 1
Second episode of grade 3 or any episode of grade 4 toxicity	Permanently discontinue therapy and remove subject from trial	Permanently discontinue therapy and remove subject from trial

Certain adverse events that are possibly immune mediated warrant special monitoring and management, and are outlined below to guide investigators.

5.2.4.1 Pulmonary:

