6.0 STUDY PROCEDURES

6.1 SCHEDULE OF ASSESSMENTS:

	Screening (within 28 days)	C1D1	C2D1	C3D1	C4D1	D1C5+	EOT¹²	Follow Up⁸
Informed Consent	X							
Review Eligibility Criteria	X							
Demographics, Height	X							
Prior and Concomitant Medications	X	X	X	X	X	X	X	
Review Adverse Events¹⁰	X	X	X	X	X	X	X	
Physical Examination, Vital Signs¹, Weight	X	X	X	X	X	X	X	
ECOG Performance Status	X	X	X	X	X	X	X	
Survival Status								X Q3m
Laboratory Assessments								
Pregnancy Test for WOBCP²	X							
CBC with diff, platelets³	X	X	X	X	X	X	X	
Comprehensive Metabolic Panel, including Alk Phos⁴	X	X	X	X	X	X	X	

	Screening (within 28 days)	C1D1	C2D1	C3D1	C4D1	D1C5+	EOT ¹²	Follow Up ⁸
LDH	X	X	X	X	X			
PSA¹¹	X	X	X	X	X	X	X	X
Testosterone¹¹	X				X		X	
TSH, free T3, free T4 (If Clinically Indicated: FSH, LH, ACTH)	X	X	X	X	X	X ⁶	X	
Therapy								
Cohorts A and B Nivolumab 3 mg/kg IV q3 wks for up to 4 doses¹³				X				
Cohorts A and B Ipilimumab 1 mg/kg IV q3 wks for up to 4 doses¹³				X				
Cohorts A and B Nivolumab 480 mg IV q4 wks for up to 23 doses¹³						X		
Cohort C Nivolumab 480 mg IV q4 wks¹⁴				X		X		
Imaging Tumor Assessments								
CT chest	X					X (q 12 wks)		
CT Abdomen/Pelvis or MRI Abdomen/Pelvis⁵	X					X (q 12 wks)		
Tc^{99m} Bone Scan (prostate only)	X					X (q 12 wks)		
QoL: BPI-SF and EORTC QLQ C30	X					X (q 12 wks)		
Correlatives								
Tumor Tissue Archival (CRPC preferred if available)	X							
Tumor Biopsy	X						X ⁷	
Research blood⁹		X	X	X		X (q 12 wks)	X	

1. Vital signs will include temperature, pulse, respirations, blood pressure; height will be obtained at screening only.
2. WOCBP: Women of child bearing potential; urine or serum pregnancy test.
3. CBC with diff includes total WBC, hemoglobin, hematocrit and differential of the WBC including absolute counts.
4. COMP or Comprehensive metabolic profile includes sodium, potassium, chloride, bicarbonate, BUN, creatinine, AST, ALT, alkaline phosphatase, total bilirubin.
5. With or without intravenous contrast, before or on associated visit. CT or MRI (preferred) brain with or without IV contrast if suspected or known brain metastases. Frequency of tumor assessments will be q12 weeks.
6. Every 42 calendar days ± 14 business days. May be delayed if infusion is not scheduled within the window.
7. Optional tissue biopsy collection at progression if subject consents; +/- 14 working days.
8. Follow up with phone call or with clinic visit.

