9. Blood for research should be collected prior to study treatment on C1D1, C2D1, C3D1 and C5D1, every 12 weeks thereafter and end of treatment.

10. Data on adverse events will be collected from the time of the initial study drug administration through 100 days after the last dose of study drug (nivolumab and/or ipilimumab) as described in Section 8.2.
11. For Cohort A only
12. End of Treatment Visit should occur within 3-4 weeks of last dose of protocol therapy.
13. Cohorts A and B (Nivolumab and Ipilimumab: 1 cycle (C) = 21 days (D) for up to 4 doses of Nivolumab (3mg/kg IV) and Ipilimumab (1mg/kg IV), then Nivolumab maintenance therapy alone (480mg IV): 1 cycle=4 weeks or 28 days (D). Total treatment time is up to 104 weeks.
14. Cohort C (Nivolumab monotherapy): 1 cycle (C) = 28 days (D) of Nivolumab monotherapy (480mg IV) for up to 104 weeks.

NOTE:

All procedures in study assessments schedule have a window of \pm 3 business days unless otherwise mentioned. Virtual clinic visits will be allowed per clinician/ subject discretion.

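### Counting scans from C5D1 puts the first on-treatment scan at week 12 in Cohorts A/B and week 16 in Cohort C, and lets A/B induction delays move it, so rPFS is not read on one clock

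*Combined protocol and SAP*

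**What the plan says.** **Scan clock.** Section 5.4 reads "Do not hold scans, continue scan schedule every 12 weeks from cycle 5 day 1 regardless of treatment delays thereafter". In the Section 6.1 table, the CT, MRI and bone scan rows are filled only at Screening and in the column for C5D1 onward. The C1D1 to C4D1, EOT and follow-up columns are blank for imaging. Footnote 5 says "Frequency of tumor assessments will be q12 weeks" without a start point, and asks that imaging be done no later than the visit it belongs to.

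**Cycle length.** Footnote 13 sets, for Cohorts A and B, "1 cycle (C) = 21 days (D) for up to 4 doses of Nivolumab (3mg/kg IV) and Ipilimumab (1mg/kg IV". Footnote 14 sets, for Cohort C, "1 cycle (C) = 28 days (D) of Nivolumab monotherapy (480mg IV) for up to 104 weeks". The same table columns serve all cohorts.

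**Delays.** Section 5.2.1 states "Treatment delay for toxicity of more than 84 days from last intended therapy will result in treatment discontinuation" of the drug responsible. Delays up to that limit are therefore allowed.

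**After treatment.** Footnote 8 says "Follow up with phone call or with clinic visit". Section 5.1.3 mentions 12-weekly imaging only for patients who resume nivolumab in follow-up: "until progression if tolerated with axial imaging as per protocol every, 12 weeks".

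**Use of the scans.** Sections 7.1.4 and 7.6 measure rPFS from start of treatment and censor event-free patients at the last scan. Section 11.3 reports the Kaplan-Meier median and the 52-week proportion, by cohort and for all patients. Cohort B's rule in Section 11.1 (3 or more responses in 15) rests on RECIST response.

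**The concern.** Radiographic progression is dated at the scan that finds it. If the scan calendar differs between cohorts, the same disease course gives different observed rPFS. Cohorts A and C are both mCRPC with the same 6-of-25 threshold, so readers will set their rPFS results side by side even though no formal comparison is planned. The all-patient summary also mixes two scan grids. Within A/B, a patient whose induction is delayed by toxicity is scanned later, so delay and observed rPFS become linked.

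A second gap sits next to the first. A patient who leaves treatment before C5 has no scheduled post-baseline scan. Without an unscheduled scan or death, that patient is censored at baseline for rPFS. In Cohort B the patient may also not be response-evaluable, because Section 7.2.1 requires a re-evaluation and exempts only progression before the end of cycle 1.

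**Working it through.** **1. The plan's own figure.** For Cohort B with X ~ Binomial(15, p), P(X ≥ 3) is 0.764 at p = 0.25 and 0.036 at p = 0.05. This reproduces the stated 76% power within the one-sided 5% limit. No stated sample size or power figure is wrong.

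**2. Scan calendar.** C5D1 falls at 4 × cycle length.

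| Case | First scan (week) | Later scans (week) |
|---|---|---|
| A/B, no delay | 4 × 3 = 12 | 24, 36, 48, 60, ... |
| C, no delay | 4 × 4 = 16 | 28, 40, 52, 64, ... |
| A/B, 42-day induction delay | 12 + 6 = 18 | 30, 42, 54, ... |
| A/B, 84-day induction delay | 12 + 12 = 24 | 36, 48, 60, ... |

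The Section 6.1 note ("All procedures in study assessments schedule have a window of" 3 business days either side) cannot absorb a four-week offset.

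**3. Observed rPFS median.** The documents give no medians, so these are assumptions: exponential progression with median m, exponential death with median OS, the same in every cohort, and no delays. Then

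S(t) = 2^(−L(t)/m) × 2^(−t/OS),

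where L(t) is the last scheduled scan at or before t (0 if none). The observed median is the first t with S(t) ≤ 0.5. Worked case, m = 20, OS = 78:

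- Cohort C at week 16: 2^(−16/20) × 2^(−16/78) = 0.498, so the median is 16.0.
- A/B just before week 24: still 0.533. At week 24: 2^(−24/20) × 2^(−24/78) = 0.352, so the median is 24.0.

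| m (OS = 78) | A/B median | C median |
|---|---|---|
| 20 | 24.0 | 16.0 |
| 23 | 24.0 | 23.7 |
| 26 | 24.0 | 28.0 |

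Over m = 14 to 39 and OS = 52 to 104 in whole weeks (26 × 53 = 1,378 combinations), C minus A/B runs from −8.0 to +4.0 weeks. The median absolute gap is 4.0 weeks, and 26% of combinations differ by less than 3 weeks. C is shorter in 41.7% and longer in 57.8%, and the mean signed gap is −0.14 weeks.

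**4. Effect of an A/B delay.** The mean lag from true progression to the scan that dates it (m = 20, no deaths) is 6.4 weeks in undelayed A/B, 7.4 in C, and 10.5 in A/B after an 84-day delay.

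**5. The 52-week proportion.** A/B is read from the week 48 scan. Week 52 is itself a Cohort C scan day (16 + 36). At m = 20, OS = 78:

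- A/B: 2^(−48/20) × 2^(−52/78) = 11.9%
- C, scan on time: 2^(−52/20) × 2^(−52/78) = 10.4%

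Over the same grid, with scans on time, C is 0.8 to 2.1 points lower. If every week-52 scan slipped just past week 52, C would be read from week 40: 2^(−40/20) × 2^(−52/78) = 15.7% in the worked case, and 2.3 to 4.7 points above A/B over the grid. That is an extreme bound.

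**6. Sampling error.** In 20,000 simulated cohorts of 25 (m = 20, OS = 78), the central 95% of observed medians is 12 to 36 weeks in A/B and 16 to 28 in C. The SD of the 52-week proportion is about 6.5 points in A/B and 6.1 in C.

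**7. Cohort B patients without a scan.** Suppose k of 15 have no post-baseline scan (the documents give no k). If they count as non-responders, the rule becomes P(X ≥ 3 | 15 − k). If they are left out and replaced, and would all have been non-responders, the rate among scanned patients becomes p/(1 − k/15).

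| k | Power, non-responders | Type I error, non-responders | Type I error, replaced |
|---|---|---|---|
| 0 | 76.4% | 0.036 | 0.036 |
| 1 | 71.9% | 0.030 | 0.043 |
| 2 | 66.7% | 0.025 | 0.052 |
| 3 | 60.9% | 0.020 | 0.063 |

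Section 5.8 replaces only undosed patients, while Section 11.2 plans 15 response-evaluable patients. The plan does not say which column applies.

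**The case against.** The strongest reply is that this is a secondary, descriptive endpoint with no cohort test, and that the gaps are smaller than sampling error at n = 25. That stands and limits the weight of the point. It does not remove it, because the schedule effect is avoidable and a wording change takes it out.

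Several stronger readings are tempting, and the documents do not support them:

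- **That the later grid favours, or penalises, Cohort C.** The sign of the median gap depends wholly on the assumed medians.
- **That Cohort C's 52-week proportion is inflated.** This needs week-52 scans to slip late. Footnote 5 asks for imaging no later than its visit, so only a late visit carrying a late scan could do it.
- **That the 12/16-week offset reaches the Cohort B rule.** Cohort B is on the 21-day induction calendar, so its undelayed first scan is week 12 on either clock. Only induction delay and missing scans touch that rule.
- **That C5 is undefined when ipilimumab stops early.** Section 5.2.1 does not number the cycles, but the Section 6.1 table marks A/B nivolumab 480 mg only from C5D1 onward, which points to the first 480 mg dose as C5.
- **That all of the Cohort B power loss is due to the schedule.** Patients who leave early through deterioration are likelier non-responders on any clock. The figures assume that each would otherwise have responded at 25%.

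Footnote 5 could be read as a week-12 scan in Cohort C, but that visit is C4D1, where imaging is blank. That is a reason to reconcile the passages. Dose delay in Cohort C is also not fully clear: the rule that missed 480 mg doses are skipped appears in Section 5.1.2, under A/B maintenance. Finally, Section 7.4.3 asks for effort to document progression after symptomatic deterioration, but it schedules no scan for a patient who leaves for toxicity.

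**Conclusion.** The concern holds at modest size. By Sections 5.4 and 6.1, the first on-treatment scan is at week 12 in A/B and week 16 in C, and A/B induction delays move it to as late as about week 24 for a single delay at the limit. Footnote 5 does not fix a start point, so the passages must be reconciled. With identical disease and no delays, the observed Cohort C median rPFS is between 8 weeks shorter and 4 weeks longer than A/B. Its 52-week proportion is about 1 to 2 points lower when scans are on time. These sizes rest on exponential times and assumed medians.

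The PSA primary endpoint and its decision rules are not affected.

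The Cohort B gap is separate. It comes from having no scheduled scan before C5 or at EOT, together with an open counting rule. The number of unscanned patients is an illustration, not a figure from the plan.

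**What to change.** 1. Reword Section 5.4, the Section 6.1 imaging rows and footnote 5 so that imaging is every 12 weeks counted from C1D1 in all cohorts, regardless of any dose delay. This gives one grid and reads the 52-week proportion from the week 48 scan everywhere.
2. Count dosed Cohort B patients without a post-baseline scan as non-responders, or report the 3-of-15 result both ways. Report their number in either case.
3. For data already collected on the C5D1 clock, add an interval-censored rPFS estimate by cohort as a sensitivity analysis beside Kaplan-Meier. It shows how much of a difference the scan grid could explain; it does not recover timing within an interval.

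**Cost.** The 12-week interval stays. Through week 104 there are 8 scans on either clock if undelayed, and 8 instead of 7 after an 84-day A/B induction delay. Some scans will fall outside dosing visits. Cohort C's first scan, which is also the bone-lesion reference in Section 7.1.5.3, comes 4 weeks earlier, so progression may be found sooner. A mid-trial change should apply to newly enrolled patients only. Because Cohort C opens after Cohort A is full, most of A would then stay on the old grid, and C could hold both. Patients who leave before week 12 unscanned remain a gap, so the Cohort B problem is reduced and made visible, not removed.

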5.5 Off Treatment Criteria

Patients will be removed from protocol specified therapy when any of the criteria listed in Section 5.4 apply. Document in the source the reason for ending protocol therapy and the date the patient was removed from treatment. All patients who discontinue treatment should comply with protocol specific follow-up procedures as outlined in Section 5.6. The only exception to this requirement is when a subject withdraws consent for all study procedures or loses the ability to consent freely.

5.6 Duration of Follow-Up

Patients will be followed every 3 months for 24 months after removal from treatment or until death, whichever occurs first. Patients removed from treatment for unacceptable adverse events will be followed until resolution or stabilization of the adverse event.

5.7 Off Study Criteria

Patients can be taken off study at any time at their own request, or they may be withdrawn at the discretion of the investigator for safety, behavioral or administrative reasons. The reason(s) for discontinuation from study or study drug therapy will be documented and may include:

- 5.7.1 Patient withdraws consent (termination of treatment and follow-up);
- 5.7.2 Loss of ability to freely provide consent through imprisonment or involuntary incarceration for treatment;
- 5.7.3 Patient is unable to comply with protocol requirements;
- 5.7.4 Treating physician determines continuation on the study would not be in the patient's best interest;
- 5.7.5 Patient becomes pregnant (pregnancy to be reported along same timelines as a serious adverse event); study patient will undergo the EOT visit and follow-up visits excluding tumor biopsy according to the activities in this protocol and study procedure assessments.
- 5.7.6 Development of second malignancy (except for basal cell carcinoma or squamous cell carcinoma of the skin) that requires treatment, which would interfere with this study;
- 5.7.7 Lost to Follow-up;
- 5.7.8 Termination of the study by The University of Michigan;
- 5.7.9 Patient completes protocol treatment and follow-up criteria.

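### Sections 5.5 and 5.7 disagree on who may leave follow-up, so survival contact could stop in patients who are doing badly and bias the secondary overall survival estimate upward

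*Combined protocol and SAP*

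**What the plan says.** Three adjacent protocol sections govern what happens after treatment stops.

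- **Section 5.5** sets the general rule: "All patients who discontinue treatment should comply with protocol specific follow-up procedures as outlined in Section 5.6". It then closes the list of exemptions: "The only exception to this requirement is when a subject withdraws consent for all study procedures or loses the ability to consent freely".
- **Section 5.6** defines that follow-up: "Patients will be followed every 3 months for 24 months after removal from treatment or until death, whichever occurs first". Section 6.1 marks survival status every 3 months, and a footnote allows a phone call or a clinic visit. PSA is also marked in the Follow Up column, with a footnote limiting it to Cohort A.
- **Section 5.7**, headed Off Study Criteria, gives patients the right to leave at their own request and adds that "they may be withdrawn at the discretion of the investigator for safety, behavioral or administrative reasons". The list that follows is introduced by "The reason(s) for discontinuation from study or study drug therapy will be documented and may include". It includes 5.7.3, "Patient is unable to comply with protocol requirements", and 5.7.4, "Treating physician determines continuation on the study would not be in the patient's best interest". Item 5.7.6 adds a second malignancy that needs treatment and would interfere with the study.

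Section 11.3 reports OS, PFS, rPFS and TTP by Kaplan-Meier, with the median and the 52-week event-free proportion. Sections 7.1.4 and 7.6 censor PFS and rPFS at the last assessment or scan, whatever the reason for leaving. No definition or censoring rule is given for OS.

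**The concern.** Section 5.5 presents its exemptions as exhaustive, and 5.7 goes beyond them. The introduction to the 5.7 list covers both leaving the study and leaving the drug, so a site cannot tell which items end contact.

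The overlap falls on patients in decline. A change in the patient's condition that rules out further treatment, in the investigator's judgment, is already an off-treatment reason in 5.4, and that route leads to 24 months of follow-up. The same patient also fits 5.7.4, under a heading that says off study. In a multi-center trial, two sites can each follow the text and treat the same patient differently.

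Kaplan-Meier assumes that censored patients have the same prospects as those still followed. If safety, compliance or best-interest withdrawals fall mainly on patients close to death, their deaths go uncounted and OS is overstated. PFS and rPFS are affected too, because both count death as an event.

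**Working it through.** **Step 1: set the sections side by side.**

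| Reason for leaving (5.7) | Exempt under 5.5? | Does 5.7 say whether follow-up ends? |
|---|---|---|
| Consent withdrawn (5.7.1) | Yes, if for all procedures | Yes: treatment and follow-up end |
| Ability to consent lost (5.7.2) | Yes | Not stated, but agrees with 5.5 |
| Non-compliance (5.7.3) | No | Not stated |
| Best-interest decision (5.7.4) | No | Not stated |
| Pregnancy (5.7.5) | No | Yes: follow-up visits continue |
| Second malignancy (5.7.6) | No | Not stated |
| Lost to follow-up, study terminated, protocol completed (5.7.7 to 5.7.9) | Not named | Contact ends by its nature |
| Discretionary: safety, behavioral, administrative | No | Not stated |

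Four rows conflict with 5.5, or at best leave the reader to guess: 5.7.3, 5.7.4, 5.7.6 and discretionary withdrawal.

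**Step 2: what the plan's own figures say.** The plan gives no design figure for OS or PFS, so there is none to reproduce. Its response-rate power does reproduce by exact binomial calculation: 80.2% for Cohort A (continue with at least 2 of 15, succeed with at least 6 of 25) and 80.7% for Cohort C (at least 6 of 25), against a stated 80%. Neither depends on this point.

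**Step 3: illustrate the possible bias.** Assumptions, none of them from the documents apart from the cohort size of 25: 12 deaths at weeks 4, 8, ..., 48; the other 13 patients followed past week 52; k of the patients who die are taken off study 3 weeks before death and their deaths are never recorded.

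- With complete follow-up, 52-week OS = 13/25 = 52.0%.
- If the k earliest deaths are lost, those patients leave the risk set before any recorded death, and the estimate is 13/(25 − k).
- If the k latest deaths are lost, only 12 − k deaths are counted with the risk set intact, and the estimate is (13 + k)/25.
- The mean is taken over every possible choice of which k deaths are lost.

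| k | Lowest | Mean | Highest |
|---|---|---|---|
| 1 | 13/24 = 54.2% | 54.9% | 14/25 = 56.0% |
| 2 | 13/23 = 56.5% | 58.0% | 15/25 = 60.0% |
| 3 | 13/22 = 59.1% | 61.2% | 16/25 = 64.0% |
| 5 | 13/20 = 65.0% | 68.3% | 18/25 = 72.0% |

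**Step 4: check by a second route.** If a share f of deaths is replaced by censoring just before death, the estimated hazard is (1 − f) times the true hazard, and Kaplan-Meier estimates S^(1 − f) in place of S.

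| True 52-week OS | f = 10% | f = 20% | f = 30% |
|---|---|---|---|
| 50% | 53.6% | 57.4% | 61.6% |
| 60% | 63.1% | 66.5% | 69.9% |

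A simulation with n = 25 and exponential survival times agrees: 53.4%, 57.2% and 61.5% for a true 50%, and 63.3%, 66.5% and 69.7% for a true 60%.

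**The case against.** The strongest reply is that 5.7 does not say follow-up ends for the disputed items. Its introduction also covers stopping the drug, only 5.7.1 expressly ends follow-up, and 5.5 can be read as filling the silence. This stands in part: for 5.7.3, 5.7.4 and 5.7.6 the text is ambiguous, not an explicit permission to end contact. It does not remove the problem. The heading and opening sentence concern leaving the study, and the authors stated that follow-up continues for pregnancy alone.

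On size, the objection is also fair. Losing 2 to 5 of 12 deaths means 17% to 42% of all deaths, each shortly after withdrawal, which is close to a worst case. One such patient moves 52% only to about 55%. Sampling error at n = 25 is about ±20 points (1.96 × √(0.52 × 0.48/25) = 0.196), so even the five-patient mean lies within it. But sampling error appears in the reported interval, and this bias does not.

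A reader might infer two stronger points that the documents do not support:

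- **That 5.7 cuts short the 100-day adverse event window.** Section 8.2 requires collection through 100 days after the last dose with no off-study exemption, and 5.6 requires patients removed for unacceptable adverse events to be followed to resolution or stabilization.
- **That 5.7 causes the loss of radiographic progression data.** The Follow Up column in 6.1 has no imaging, so a patient followed exactly as 5.5 requires has no scheduled scan there either. Only the death component of PFS and rPFS can be lost through 5.7.

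**Conclusion.** The conflict between 5.5 and 5.7 is in the current text and should be reconciled. It lets survival contact stop in patients who are doing badly, and the resulting bias in OS, and in the death component of PFS and rPFS, would be upward.

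The size cannot be established from the documents, which give no death rate, withdrawal rate or OS censoring rule. Under the assumptions shown, the 52-week estimate rises by about 3 points if one of 12 deaths is lost and by about 16 points if five are. If sites already apply 5.5 to everyone, the bias from this source is close to zero.

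The affected endpoints are secondary, descriptive and single-arm. The primary PSA-response decision rule is not affected.

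**What to change.** Reconcile 5.5 and 5.7 on follow-up. State in 5.7 that survival follow-up ends only for:

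- withdrawal of consent for all procedures;
- loss of the ability to consent;
- loss to follow-up;
- study termination;
- completion of follow-up.

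State also that patients leaving for any other 5.7 reason, including discretionary withdrawal, remain in the 5.6 survival-status follow-up, and make 5.5 refer to the same list.

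Leave the treatment-stopping criteria in 5.4 unchanged. Moving 5.7 items there would go further than needed: 5.5 makes removal from therapy mandatory when a 5.4 criterion applies, whereas withdrawal under 5.7 is discretionary.

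The cost is an amendment to the wording and a few three-monthly contacts by phone or clinic visit, plus PSA where 6.1 marks it. Sections 5.5 and 5.6 already require these contacts. The change is best made early, because vital status may not be recoverable once a site has closed a patient's follow-up.
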